9.4. Data Sources

The CorEvitas RA Registry is an observational registry and therefore collects patient and physician data at patient clinical visits with the rheumatologist. Unlike clinical studies, visits are not timed at exact uniform time periods. Thus, time period definitions for the current study need to accommodate this unique feature of observational registries.

“Index visit” is defined as the visit when tofacitinib was initiated, ie, first ever use of tofacitinib. Only initiations at or after enrollment into the Registry are included.

A “6-month” follow-up is defined as a clinical visit to the rheumatologist 3 to 9 months from the enrollment visit in accordance with the Registry protocol.

Initiations between visits

If tofacitinib is initiated between visits, then baseline variables from the visit prior to the initiation of tofacitinib will be used, as long as the prior visit occurred within four months of the tofacitinib start date. Initiations that occur between visits and where the prior visit is greater than 4 months from the initiation will be excluded.

Multiple visits in the same time window

Given the observational nature of the data, it is possible for patients to have more than one visit that falls within a given follow-up period's allowed time window. For example, a patient might have a visit with outcomes collected at 5 months and then 9 months, both of which would qualify as a "6-month" visit. In that case, the latest visit will be chosen as the "6-month" follow-up since we would like to consider the longest follow-up possible. The exception to this rule is if values for the primary outcome are unavailable for the latest visit, in which case the first visit will be used instead.

Discontinuations prior to follow-up

For patients who discontinued tofacitinib prior to follow-up and who do not switch to another drug, the clinical or patient-reported outcome value at the follow-up visit will be used. If a patient discontinues and switches to another biologic/tsDMARD, the value at the switch visit, if available, will be used; otherwise, the value will be set to missing.

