4.4.3. Time Period Definitions

The CorEvitas RA Registry is an observational registry and therefore collects patient and physician data at patient clinical visits with the rheumatologist. Unlike clinical studies, visits are not timed at exact uniform time periods. Thus, time period definitions for the current study need to accommodate this unique feature of observational registries.

“Index visit” is defined as the visit when tofacitinib was initiated, i.e. first ever use of tofacitinib. Only initiations at or after enrollment into the Registry are included.

A “6-month” follow-up is defined as a clinical visit to the rheumatologist 3 to 9 months from the enrollment visit in accordance with the Registry protocol.

4.4.3.1. *Initiations between visits*

If tofacitinib is initiated between visits, then baseline variables from the visit prior to the initiation of tofacitinib will be used, as long as the prior visit occurred within four months of the tofacitinib start date. Initiations that occur between visits and where the prior visit is greater than 4 months from the initiation will be excluded.

4.4.3.2. *Multiple visits in the same time window*

Given the observational nature of the data, it is possible for patients to have more than one visit that falls within a given follow-up period’s allowed time window. For example, a patient might have a visit with outcomes collected at 5 months and then 9 months, both of which would qualify as a “6-month” visit. In that case, the latest visit will be chosen as the “6-month” follow-up since we would like to consider the longest follow-up possible. The exception to this rule is if values for the primary outcome are unavailable for the latest visit, in which case the first visit will be used instead.

4.4.3.3. *Discontinuations prior to follow-up*

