4.4.6.6. Medications

- Previous drug therapies
 - Number of prior csDMARDs, (incl: MTX, Arava, Azulfidine, Plaquenil, Cyclosporine, Imuran, Minocin, Cuprimine, Ridaura)
 - Number of prior bDMARDs/JAKis (incl: TNFi: Enbrel, Humira, Remicade, Cimzia, Simponi; non-TNFi: Orencia, Actemra, Rituxan, Kineret, Kevzara; JAKis: Olumiant, Rinvoq)
 - History of prednisone use
- Line of therapy at tofacitinib initiation:
 - Number (%) with 2 prior biologics (I.e., RTX + 1 other biologic)
 - Number (%) with 3 prior biologics (I.e., RTX + 2 other biologics)
 - Number (%) with 4+ prior biologics (I.e., RTX + 3+ biologics)
- Concomitant therapies
 - Concomitant medications (none, MTX only, nonMTX csDMARD only, MTX & nonMTX csDMARD)
 - Current prednisone use
 - Prednisone dose, among current users
- Detailed description of RTX use:
 - Number (%) using RTX directly before tofacitinib
 - Duration of prior RTX use, where available
 - Line of therapy of RTX
 - Year of RTX discontinuation
- Total number (%) of discontinuations
- Reason for Discontinuation of RTX (among those who discontinue

RTX at or after enrollment in registry)

- Number of patients with at least 1 reason reported
- Total number of reasons
- %Safety, %Efficacy, %Cost/Insurance, %Other reasons
- Tofacitinib initiation year

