4.4.7. Analysis Plan

4.4.7.1. Aim 1: *Describe the characteristics of tofacitinib initiators with a history of rituximab exposure, at time of tofacitinib initiation*

Descriptive statistics for the variables listed in [Section 4.4.6](#) will be provided for all tofacitinib initiators with history of rituximab use. All variables will be measured at the index visit, as defined above. Categorical covariates will be described by frequency distribution while continuous covariates will be expressed in terms of their mean and standard deviation or median and interquartile range (IQR) as appropriate.

4.4.7.2. Aim 2: *Describe 6-month outcomes for tofacitinib initiators with a history of rituximab exposure*

Descriptive statistics for index visit characteristics will be provided for the subsets of patients included in this Aim (tfacitinib initiators who have a 6-month follow-up visit), as described in Aim 1.

Analyses of outcomes at the 6-month follow-up after tofacitinib initiation will be descriptive. Primary and secondary outcomes will be described as mean absolute differences for continuous measures and as frequencies and proportions for dichotomous measures, with corresponding 95% confidence intervals (95% CI). Mean absolute difference will be defined as the value at the 6-month follow-up visit minus the value at baseline. The number of patients that discontinue tofacitinib will also be summarized. A subgroup analysis related to the outcomes for Aim 2 will be carried out focused on patients who used rituximab immediately prior to tofacitinib.

All analyses will be conducted using Stata Release 16 (StataCorp LLC, College Station TX) and/or R Version 4.0.3 (The R Foundation for Statistical Computing, Vienna Austria).

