8. TABLES

Table 1: Patient Demographics and Clinical Characteristics at Index Visit, Primary Cohort and Subset with 6-month Visit (Secondary analysis cohort)

| Characteristics | Primary Cohort | Subset w/ 6-month visit |
|--|----------------|-------------------------|
| Total (N) | N = | N = |
| Demographics/socioeconomic characteristics | | |
| Age in years, mean (SD) | | |
| Gender – female, n (%) | | |
| Race, n (%) White African American Asian Other | | |
| Health insurance type, n (%) Private, n (%) Medicare, n (%) Medicaid, n (%) No Insurance, n (%) | | |
| Education, n (%) College graduate or higher | | |
| Work status, n (%) Full time Part time Work at home Student Disabled Retired Unemployed | | |
| Lifestyle characteristics | | |
| Smoking history, n (%) Never smoked Former smoker Current smoker | | |
| Current alcohol use, n (%) None/<1 drink per week 1-3 drinks per week 1-2 drinks per day > 3 drinks per day | | |
| Body weight (kg), mean (SD) | | |

| | | |
|--|--|--|
| BMI (kg/m2) continuous, mean (SD) | | |
| BMI¹ (kg/m2) categorical, n | | |
| (%) BMI <25 (underweight/normal) | | |
| BMI 25 – <30 (overweight) | | |
| BMI > 30 (obese) | | |
| History of comorbidities, n (%) | | |
| Malignancy ² | | |
| Serious Infection ³ | | |
| Tuberculosis (active or latent) | | |
| Cardiovascular disease ⁴ | | |
| Hypertension | | |
| Diabetes Mellitus | | |
| Interstitial Lung Disease (ILD)/Pulmonary fibrosis | | |
| Disease activity characteristics | | |
| Duration of RA (years) continuous, mean (SD) | | |
| Age at onset of RA (years) continuous, mean (SD) | | |
| CDAI continuous, mean (SD) | | |
| CDAI categorical, n (%) | | |
| Remission (CDAI < 2.8) | | |
| Low (2.8 ≤ CDAI < 10) | | |
| Moderate (10 ≤ CDAI < 22) | | |
| High (22 ≤ CDAI) | | |
| mHAQ continuous, mean (SD) | | |
| Tender Joints continuous, mean (SD) | | |
| Swollen Joints continuous, mean (SD) | | |
| Physician Global Assessment continuous, mean (SD) | | |
| Treatment characteristics | | |
| Concomitant therapy, n (%) | | |
| Monotherapy | | |
| Combination with MTX only | | |
| Combination with nonMTX csDMARD only | | |
| Combination with MTX & nonMTX csDMARD | | |
| Prednisone | | |
| Prednisone dose, among current users | | |
| Prior csDMARD Use, n (%)⁵ | | |
| 0 previous csDMARDs | | |
| 1 previous csDMARD | | |
| ≥2 previous csDMARDs | | |

| | | |
|---|--|--|
| Prior bDMARD Use, n (%)⁶ 0 previous bDMARDs 1 previous bDMARD ≥2 previous bDMARDs | | |

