| Line of therapy at tofacitinib initiation: 2 prior biologics (i.e., RTX + 1 other biologic) 3 prior biologics (i.e., RTX + 2 other biologic) 4 prior biologics (i.e., RTX + 3 other biologic) | | |
| Duration of tofacitinib use, continuous, mean (SD) | | |
| Rituximab as immediate prior treatment, n (%) Duration of prior RTX use, n (%) Line of Therapy at rituximab initiation Rituximab Discontinuation Year | | |
| Reasons for discontinuing RTX, categorical, n (%)⁷ Efficacy, n/ N1 (%) Safety, n/ N1 (%) Insurance, n/ N1 (%) Active disease, n/ N1 (%) Other reasons, n/ N1 (%) | | |
| Tofacitinib initiation year 2012-2013 2014-2015 2016-2017 2017-2018 2019-2022 | | |
| Patient reported measures* | | |
| Patient global assessment (VAS range 0-100), n mean (SD) median (IQR) | | |
| Modified HAQ, n mean (SD) median (IQR) | | |
| Patient fatigue (VAS range 0-100), n mean (SD) median (IQR) | | |
| Patient pain (VAS range 0-100), n mean (SD) median (IQR) | | |

| EQ-5D-3L categorical domains | | |
|--|--|--|
| Walking, n (%) Self-care, n (%) Usual activities, n (%) Pain and discomfort, n (%) Anxiety and depression, n (%) | | |

1. Based on the CDC cut-offs for normal/underweight (under 25); Overweight (25.0 – 29.9); and Obese (30.0 and above)
2. Cancer includes lymphoma, lung, breast, skin [basal cell, squamous cell, melanoma], and any other cancers
3. Infections include Joint/bursa, cellulitis/skin, sinusitis, Candida, diverticulitis, sepsis, pneumonia, bronchitis, gastroenteritis, meningitis/encephalitis, urinary tract, upper respiratory, TB, and other. Infections resulting in Hospitalization or administration of IV antibiotics indicates serious infection
4. Cardiovascular disease includes baseline history of any of the following: MI, stroke, acute coronary syndrome, coronary artery disease, CHF, revascularization procedure including percutaneous coronary intervention [PCI], coronary artery bypass grafting [CABG] or coronary artery stents, ventricular arrhythmia, cardiac arrest, unstable angina, peripheral ischemia, peripheral arterial disease, hypertension, other CVD, Deep Venous Thrombosis (DVT), and Transient Ischemic Attack (TIA).
5. Prior non-biologic systemic use count does not include the current non-biologic systemic therapy, if applicable
6. Prior biologics count does not include subject's current biologic

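### For tofacitinib starts between visits, treatment variables are read at a visit up to four months earlier, so concomitant therapy can describe the pre-tofacitinib regimen and the prior-biologic count can miss the drug being replaced

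*SAP*

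**What the plan says.** SAP 4.4.3 sets the reference point for baseline: "Index visit” is defined as the visit when tofacitinib was initiated, i.e. first ever use of tofacitinib". A start between visits has no such visit, so 4.4.3.1 supplies a substitute: "If tofacitinib is initiated between visits, then baseline variables from the visit prior to the initiation of tofacitinib will be used". The only condition attached is a limit on how old that visit may be: "as long as the prior visit occurred within four months of the tofacitinib start date". Protocol 9.4 matches it: "baseline variables from the visit prior to the initiation of tofacitinib will be used, as long as the prior visit occurred within four months".

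For Aim 1, SAP 4.4.7.1 covers the whole variable list in 4.4.6 and adds: "All variables will be measured at the index visit, as defined above". That list includes the medication block in 4.4.6.6: "Concomitant medications (none, MTX only, nonMTX csDMARD only, MTX & nonMTX csDMARD", current prednisone and its dose, counts of prior csDMARDs and prior bDMARDs/JAK inhibitors, line of therapy, and use of rituximab directly before tofacitinib.

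The prior-bDMARD rows in Table 1 begin "0 previous bDMARDs 1 previous bDMARD" and end with a class for two or more. Footnote 6 reads "Prior biologics count does not include", followed by the subject's current biologic. Footnote 5 treats current non-biologic systemic therapy in the same way.

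**The concern.** Disease activity and patient-reported measures exist only at visits, so the last visit before the start is a reasonable stand-in for them. Treatment is different. By construction, a between-visit starter was not yet on tofacitinib at that visit and may still have been on the drug that tofacitinib replaced. Two consequences follow from a literal reading.

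- Concomitant csDMARD and prednisone are those that accompanied the earlier regimen. Monotherapy or combination is assigned before any change made around the switch.
- If current in footnote 6 is judged at the earlier visit, the biologic about to be replaced is left out and the prior count is one too low.

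Patients who start at a visit are described at the start itself, so one Table 1 column could mix two reference times. The primary objective is a description of patients at initiation, and treatment background is a central part of it. The immediate-prior-rituximab variable also defines the Table 4 subgroup, and no derivation is given for it in between-visit starters.

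**Working it through.** **1. The texts side by side.** SAP 4.4.3.1 and Protocol 9.4 speak of baseline variables without limiting the type. SAP 4.4.7.1 sends all of 4.4.6, medications included, to the index visit. By contrast, SAP 4.4.3.3 on discontinuations restricts itself to the outcomes listed in 4.4.5.2. Section 4.4.3.1 has no such restriction, and none appears elsewhere.

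**2. The plan's own figures.** SAP 4.4.9 and Protocol 9.5 give 8 patients with rituximab only and 365 with rituximab plus at least one other biologic. 8 + 365 = 373; 8/373 = 2.1%; 365/373 = 97.9%. The stated 2% and 98% are reproduced, and nobody is classed at zero.

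**3. Effect of dropping one biologic in the Table 1 rows.**

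| True prior biologics | Count if the replaced drug is left out | Row change |
|---|---|---|
| 1 (rituximab only) | 0 | 1 to 0, impossible given the prior-rituximab criterion |
| 2 | 1 | ≥2 to 1 |
| 3 or more | 2 or more | none |

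At most 8 of about 373 patients could reach the zero row. The documents do not split the 365 into those with exactly two prior biologics and those with more, so the number who could move from ≥2 to 1 is unknown.

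**4. Size, on assumptions only.** Let f be the share of starts that fall between visits, and m the share of those with a drug change between the prior visit and the start. The documents give neither. Assume f from 10% to 50% and m from 25% to 100%. The number with some treatment variable misdescribed is N × f × m.

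- Aim 1, N = 376 with baseline CDAI: 376 × 0.10 × 0.25 = 9.4 (2.5%) up to 376 × 0.50 × 1.00 = 188 (50%).
- Six-month subset, N = 107: 107 × 0.10 × 0.25 = 2.7 up to 107 × 0.50 × 1.00 = 53.5.
- Rituximab-only patients who could fall to zero, applying the same f and m and the earlier-visit reading of footnote 6: 8 × 0.10 × 0.25 = 0.2 up to 8 × 0.50 × 1.00 = 4.0.

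The width of these ranges shows that the size is unknown. They are not estimates.

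**The case against.** The strongest reply concerns the prior count. Footnote 6 does not tie current to the earlier visit, and in a table of tofacitinib initiators it can fairly mean tofacitinib. The line-of-therapy and immediate-prior-rituximab items in 4.4.6.6 are labelled relative to tofacitinib, and the feasibility counts put nobody at zero. The zero row may simply come from a generic table shell. All of this stands, so the undercount is a possible result of the wording and not a certain one. It does not settle the matter. A label states the intended time without giving a derivation, the registry eligibility text in SAP 4.4.1 names biologics and JAK inhibitors as separate classes, and the feasibility counts do not fix the final programming.

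A reader might go further and infer that Table 1 shows the old regimen for between-visit starters in general, or that prior biologic experience is biased downward by a known amount. The documents support neither. The error needs a change of therapy in the interval and, for the count, one particular reading of footnote 6. Nothing says how often patients were still on their last biologic at the prior visit. The cap at two or more also means that a lowered count often leaves the row unchanged.

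A second reply concerns feasibility. The four-month rule needs a tofacitinib start date, but that does not show that csDMARD or prednisone dates are complete. SAP 4.4.6.6 asks for rituximab duration only where available, and 4.5.2 warns of incomplete recall of medication history before enrollment. Taking concomitant therapy from the first visit after the start could bring later changes into baseline. Both points stand and limit the remedy for concomitant therapy.

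That the study is descriptive and the rule disclosed does not remove the point, because the description at initiation is the primary result.

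**Conclusion.** The concern holds in a conditional form. As written, the rule gives the wrong reference time for concomitant csDMARD and prednisone in between-visit starters whose therapy changed between the prior visit and the start. That follows directly from the text and needs no assumption about footnote 6. The prior-bDMARD count can be one too low only if current is read at the earlier visit. Line of therapy and immediate-prior rituximab are less clearly affected because their labels point to tofacitinib.

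The size cannot be derived from the documents. The firm bounds are that only patients with one or two true prior biologics can change row, and that at most 8 of about 373 could enter the zero row. The rule should be corrected before Table 1 is produced. The look-back for CDAI and patient-reported measures is not in question.

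**What to change.** In SAP 4.4.3.1 and Protocol 9.4:

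1. Limit the prior-visit rule to clinical, patient-reported and other visit-measured variables.
2. Define the prior bDMARD/JAK-inhibitor count, line of therapy and immediate-prior rituximab as of the tofacitinib start date, counting every biologic or JAK inhibitor started before that date. Reword footnote 6 so that current means tofacitinib, and check that the zero row is empty. Use the same derivation for the Table 4 subgroup.
3. Derive concomitant csDMARD and prednisone as of the start date from recorded start and stop dates where these exist. Where they do not, keep the prior-visit value and flag it. Do not use values that changed after the start.
4. Report the number of between-visit starts, so that readers can judge how much of Table 1 depends on the rule.

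The cost is a wording change in both documents and some extra programming. Some concomitant-therapy values will remain flagged where dates are missing. CDAI and patient-reported baselines do not change.

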9.2.1. Inclusion Criteria

Patients must meet all of the following inclusion criteria to be eligible for inclusion in the study:

Objective 1 Inclusion Criteria:

- Enrolled in the CorEvitas RA Registry and initiated tofacitinib on or after November 2012.
- Initiate tofacitinib (defined as first ever use of tofacitinib) at Registry enrollment visit or at a Registry follow-up visit after November 2012.
- Have prior use of rituximab.
- Have Clinical Disease Activity Index (CDAI) measured at baseline.

Objective 2 Inclusion Criteria:

- Enrolled in the CorEvitas RA Registry and initiated tofacitinib on or after November 2012.

- Initiate tofacitinib (defined as first ever use of tofacitinib) at Registry enrollment visit or at a Registry follow-up, after November 2012.
- Have prior use of rituximab.
- Have CDAI measured at baseline and appropriate follow-up visit.
- Have any of the following:
 - a. A 6-month follow-up visit with persistent use of tofacitinib.
 - b. A 6-month follow-up visit with a tofacitinib discontinuation occurring prior to the 6-month visit, with no new biologic systemic drug used prior to the 6-month study visit.
 - c. A study visit at or prior to the 6-month window with a tofacitinib discontinuation occurring at the study visit.
 - d. (Sensitivity analysis only) Any tofacitinib discontinuation prior to the 6-month study window.

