4.4.2. Study Population of Interest

The primary analysis (Aim 1) will include patients that initiated tofacitinib at or post enrollment into the Registry and after tofacitinib approval, and who have any prior use of RTX. The secondary analysis (Aim 2) will include the subset of patients from the primary analysis who also have a 6-month follow-up visit (as defined below) after tofacitinib initiation with clinical and patient reported outcomes.

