For patients who discontinue tofacitinib prior to 6 months window, the clinical or patient-reported outcome (listed in Section 4.4.5.2) will be imputed via last observation carried forward (LOCF), using only registry visits that occur before the discontinuation. Specifically, outcomes observed at a registry visit in the 6-month window will use data collected at that visit with the following exception. Patients that discontinue tofacitinib at a registry visit prior to the six month window will have the outcomes collected at that registry visit carried forward as the outcomes in the 6-month window. A patient that discontinues tofacitinib between registry visits will have the outcomes collected at the registry visit prior to the discontinuation carried forward as the 6-month outcome.

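### Protocol 9.4 and SAP 4.4.3.3 give different 6-month values for some patients who stop tofacitinib; plainly read, the SAP rule can carry the baseline visit forward as the outcome

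*SAP*

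**What the plan says.** Aim 2 describes change from baseline to 6 months. Change in CDAI is its primary outcome; MCID achievement, HAQ, pain, fatigue and discontinuations are secondary (SAP 4.4.5.2). SAP 4.4.7.2 defines the change score: "Mean absolute difference will be defined as the value at the 6-month follow-up visit minus the value at baseline".

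**Protocol 9.4.** For patients who stop and do not switch, "the clinical or patient-reported outcome value at the follow-up visit will be used". For those who switch, "the value at the switch visit, if available, will be used; otherwise, the value will be set to missing".

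**SAP 4.4.3.3.** Its opening sentence applies last observation carried forward (LOCF) to stops before the window and draws only on visits that precede the stop. The next sentence says that a visit in the window supplies its own data, subject to an exception. A stop at a visit before the window has that visit carried forward. The section ends with stops between visits: "A patient that discontinues tofacitinib between registry visits will have the outcomes collected at the registry visit prior to the discontinuation carried forward". That value then serves for month 6.

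**Baseline.** When tofacitinib starts between visits, "then baseline variables from the visit prior to the initiation of tofacitinib will be used", provided that visit was no more than four months earlier (SAP 4.4.3.1).

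**Who is in Aim 2.** SAP 4.4.2 takes those in the primary cohort "who also have a 6-month follow-up visit (as defined below) after tofacitinib initiation with clinical and patient reported outcomes". Protocol 9.2.1, Objective 2 criterion (b), admits "A 6-month follow-up visit with a tofacitinib discontinuation occurring prior to the 6-month visit". It adds a condition on switching: "with no new biologic systemic drug used prior to the 6-month study visit".

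**Limitations text.** SAP 4.5.2 and protocol 9.9 both say that bias from stopping is reduced by using follow-up values for patients who stop and switch-visit values for patients who switch.

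**The concern.** Both rules are current text. The LOCF rule entered the SAP on 06-Jan-2023, protocol version 3.0 of 13 January 2023 kept the other rule, and the SAP was amended again on 04-May-2023 with LOCF in place. Two analysts following the two documents would report different Aim 2 results from the same data.

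The SAP rule also puts no lower limit on the date of the carried visit. If the last visit before the stop is the baseline visit, the reported 6-month change is baseline minus baseline. It enters the mean as a zero and counts as MCID not achieved, with nothing measured on treatment.

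A reader of the report could not see this. SAP 4.4.7.2 plans no comparison of the two rules, Tables 3 and 4 have no count of carried values, and the limitations text would credit a safeguard that SAP 4.4.3.3 does not apply to these patients.

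**Working it through.** The plan gives no figure to reproduce: the study is descriptive, and neither document states an SD, an expected change or a number of discontinuers.

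**Step 1. Apply the rules to example histories.** CDAI values are invented and baseline is 30 throughout. Months count from tofacitinib start, and the 3-to-9-month window is assumed to do so too. The second SAP column is the reading in which an in-window value is kept unless the stop was at a visit before the window.

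| History | SAP, plain reading | SAP, other reading | Protocol 9.4 |
|---|---|---|---|
| A. Stop at month 2 between visits, no switch; month-6 CDAI 34 | 30-30 = 0 | 34-30 = +4 | +4 |
| B. As A, baseline visit 3 months before start | 0 | +4 | +4 |
| C. Stop at month 2 between visits, switch at the month-6 visit (34) | 0 | +4 | +4 |
| D. Stop and switch at the month-2 visit (28); month-6 CDAI 20 | 28-30 = -2 | -2 | -2 |
| E. Stop at the month-2 visit (28), no switch; month-6 CDAI 20 | -2 | -2 | 20-30 = -10 |
| F. Stop and switch between visits near month 2; month-6 CDAI 20 | 0 | -10 | missing |

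On the plain reading the documents differ in A, B, C, E and F and agree in D. On the other reading they still differ in E and F. The zero arises only for stops between visits with no visit between start and stop (A, B, C, F).

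**Step 2. Does a zero replace a measurement?** In A and B, yes: SAP 4.4.2 requires a 6-month visit with outcomes, and protocol criterion (b) admits non-switchers who stopped before it.

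**Step 3. The window anchor.** Protocol 9.4 and SAP 4.4.3 count the 3 to 9 months from the enrollment visit. If the earlier visit in B is the enrollment visit, the stop falls at month 2+3 = 5 and the follow-up visit at month 6+3 = 9. The stop is then inside the window. The opening sentence of SAP 4.4.3.3 limits LOCF to stops before the window; its last sentence has no such limit.

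**Step 4. Effect on the mean.** Let d be the share whose baseline is carried forward, x their mean change at the in-window visit, and m the mean change in the others.

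- Baseline carried: (1-d)m + d*0
- Observed value: (1-d)m + d*x
- Difference: -d*x, whatever m and the SD are

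| d (patients of 107) | x = +3 | x = -6 |
|---|---|---|
| 5% (about 5) | -0.15 | +0.3 |
| 10% (about 11) | -0.3 | +0.6 |
| 20% (about 21) | -0.6 | +1.2 |
| 30% (about 32) | -0.9 | +1.8 |

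A negative entry makes the mean look too favourable; a positive one understates improvement. Both d and x are assumptions. The 107 is the approximate number with CDAI at baseline and 6 months in the 31 March 2021 data cut (SAP 4.4.9).

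**Step 5. Effect on the interval.** Assume m = -8, SD 13, d = 20%, n = 107, t = 1.983.

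- Baseline carried: variance 0.8*169 + 0.16*64 = 145.44; half-width 1.983*sqrt(145.44/107) = 2.31
- Observed, x = +3: variance 169 + 0.16*121 = 188.36; half-width 2.63
- Observed, x = -6: variance 169 + 0.16*4 = 169.64; half-width 2.50

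Narrowing is usual but not general. The carried interval is wider when (1-d)*x*(2m-x) exceeds SD squared. With m = -12, SD 10, x = -10 and d = 10%, the left side is 0.9*140 = 126 against 100, and the interval is 1.3% wider.

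**Step 6. Effect on MCID.** The thresholds are 1, 6 and 12, and a change of 0 exceeds none of them. Each affected patient who had achieved MCID at the in-window visit lowers the proportion by 1/107 = 0.93 percentage points. This applies to Table 3 only: Table 4 is a subgroup, and its MCID row also leaves out patients in remission at baseline.

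**The case against.** **The SAP may keep in-window values.** SAP 4.4.3.3 says that visits in the window use their own data and announces a single exception; the case that follows at once is a stop at a visit before the window. If that is the only exception, a patient who stopped between visits and has an in-window visit keeps the observed value, and few or no zeros arise. This stands as a possible reading. The restriction to visits before the stop, and the last sentence of the section, favour the plain one. The zero should therefore be called possible, not certain.

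**The SAP is allowed to differ.** Protocol 9.7 lets the SAP modify the protocol, so the SAP rule is probably the operative one. A reader might infer a breach, because 9.7 also sends major changes to primary endpoint definitions to a protocol amendment. The documents do not establish that: change in CDAI is primary only within a secondary, descriptive objective.

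**Treating early stoppers as unchanged is a recognised convention.** It is defensible if chosen and labelled as such. It is not what the limitations text describes.

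**Two further inferences go too far.** One is that the sensitivity analysis dropped from the SAP would have exposed the problem. As the amendment table describes it, that analysis imputed non-response for binary outcomes when no switch value was available, so it would not have shown baseline being carried. The other is that everyone who switches between visits is outside Aim 2. Criterion (b) bars only a new biologic, protocol 9.4 speaks of biologics and tsDMARDs, and SAP 4.4.2 does not restrict switchers.

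**Conclusion.** The conflict between protocol 9.4 and SAP 4.4.3.3 is real and survives both readings of the SAP. It affects patients who stop between registry visits, and non-switchers who stop at a visit before the window and have a later visit inside it. On the plain reading, the SAP also allows baseline to be reported as the 6-month outcome. The mitigation sentence in SAP 4.5.2 and protocol 9.9 does not match the SAP rule for these patients.

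The size for this study is unknown. The shift is -d*x, and every input except 107 is assumed. With m = -8 and SD 13, it reaches the width of one CI arm only if 39 of 107 patients (36%) are affected at x = -6, or 64 (60%) at x = +3. The documents do not support a claim of bias in a known direction, or of a large effect. The harm is to reported descriptive estimates, since no hypothesis is tested. It should be corrected because the report could not otherwise show what its 6-month values are.

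**What to change.** 1. State one discontinuation rule identically in protocol 9.4 and SAP 4.4.3.3. Say whether a measured in-window value is ever overridden, and cover stops between visits both before and inside the window. The rule needs a clear window anchor to work.
2. If LOCF is kept, do not present an index or pre-start value as a measured 6-month outcome. Allow carry-forward only from a visit after tofacitinib start, and state how patients without such a visit are handled.
3. Show the observed-value analysis (the protocol 9.4 rule) beside LOCF in Tables 3 and 4. Which of them is the main analysis is the sponsor's choice of estimand.
4. Report in both tables how many values were carried forward and how many of those were baseline values.
5. Correct or delete the mitigation sentence in SAP 4.5.2 and protocol 9.9 so that it matches the rule used.

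The cost is wording changes in two documents, count columns and one extra run of Tables 3 and 4. No new data collection is needed: under SAP 4.4.2 the patients in the Aim 2 set already have in-window values.
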